## 4.2 EFFICACY/EFFECTIVENESS ENDPOINT(S)

There is no pre-specified endpoint, but the study collects information from adult subjects prescribed Genotropin in clinical practice.

Each patient will be classified according to his/her IGF-I assessments as follows (in hierarchy);

1. If any of the assessments of IGF-I after Swegho baseline visit, are less than the lower limit of normal (LLN), the patient will be defined as “*IGF-I LLN*”.
2. Else if any of the assessments of IGF-I after Swegho baseline visit, are greater than the upper level of normal (ULN), the patient will be defined as “*IGF-I ULN*”.
3. Else if the patient has no IGF-I reported after Genotropin start, the patient will be defined as “*IGF-I unknown*”.
4. Else the patient will be defined as “*within ref range*”.

Where appropriate, the summaries will be presented by subgroups as defined above.

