9.10. Study size

This is a descriptive study without a pre-specified hypothesis and calculation of sample size is not applicable. Approximately 900 patients are expected to be included.

The study is planned to continue for 5 years and each patient entering the study will be included for the whole time period if not prematurely with-drawn. Hence the total number will be in the range of 900 patients (600 from KIMS® and 250 new adult patients and 50 from the confirmed childhood onset GHD population).

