11.2. Reporting period

For each patient, the safety event reporting period begins at the time of the patient's first dose of Genotropin® or the time of the patient's informed consent if s/he is already exposed to Genotropin®, and lasts through the end of the observation period of the study, which must include at least 28 calendar days following the last administration of a drug under study; a report must be submitted to Pfizer Safety (or its designated representative) for any of the types of safety events listed in the table above occurring during this period. If a patient was administered a drug under study on the last day of the observation period, then the reporting period should be extended for 28 calendar days following the end of observation. Most often, the date of informed consent is the same as the date of enrollment. In some situations, there may be a lag between the dates of informed consent and enrollment. In these instances, if a patient provides informed consent but is never enrolled in the study (e.g., patient changes his/her mind about participation), the reporting period ends on the date of the decision to not enroll the patient.

If the investigator becomes aware of a SAE occurring at any time after completion of the study and s/he considers the SAE to be related to Genotropin®, the SAE also must be reported to Pfizer Safety.

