## 2.2 STUDY OBJECTIVES

The overall purpose of this study is:

- 1) To assess the long term treatment outcomes of GH treatment in patients who are prescribed and treated with Genotropin.

CCI

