## 3 ANALYSIS SETS/POPULATIONS

### 3.1 FULL ANALYSIS SET

The full analysis population (FAS) will consist of all correctly enrolled patients who received at least one dose of Genotropin. Erroneously enrolled patients are excluded from FAS since these patients did not meet the inclusion criteria or meet an exclusion criterion (which was discovered after enrollment to the study).

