### 4.3.1 Adverse Events

Definitions for the different types of AE including the definition for Serious Adverse Events (SAEs) are given in the study protocol.

The following variables has been collected for each AE and SAE; a diagnosis is preferred as event term rather than only describing symptoms, the date when the AE started and stopped, whether the AE is serious or not, causality assessment, action taken with regard to Genotropin®, AE caused patient to discontinue study and outcome.

All AEs will be classified by System Organ Class (SOC) and Preferred Term (PT) according to the available MedDRA Version.

The seriousness criterion will also be listed for SAEs.

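### SAP 4.1 and 4.2 do not separate IGF-I values taken on Genotropin from those taken after stopping, so one off-drug low value could set a patient's label for the whole study

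*SAP*

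**What the plan says.** The SAP's objective is "To assess the long term treatment outcomes of GH treatment in patients who are prescribed and treated with Genotropin". SAP 4.2 states that there is no pre-specified endpoint, then defines one patient-level classification, applied in order. Rule 1 (low) reads "If any of the assessments of IGF-I after Swegho baseline visit, are less than the lower limit of normal (LLN". Rule 2 (high) reads "Else if any of the assessments of IGF-I after Swegho baseline visit, are greater than the upper level of normal (ULN". Rule 3 (unknown) begins "Else if the patient has no IGF-I reported after Genotropin start". Everyone else is within the reference range. Only rule 3 mentions Genotropin, and it refers to the start of treatment, not the end.

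For the yearly summaries, SAP 4.1 drops visits in the first 6 months after baseline and takes one visit per yearly window. The visit is chosen by whether it has an IGF-I value and then by closeness to the target date. Treatment status plays no part.

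The full analysis set is "all correctly enrolled patients who received at least one dose of Genotropin". The missing-value rule in SAP 5 deals only with values that are absent.

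Protocol 9.3 requires Genotropin to be prescribed at inclusion. Protocol 9.5 runs data collection until withdrawal from the study, and 9.10 adds that "each patient entering the study will be included for the whole time period if not prematurely with-drawn".

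**The concern.** Leaving the drug and leaving the study are different events here, and the effectiveness rules react only to the second. Because the low rule stands first in the hierarchy, a single low value decides the label whatever the patient's other values show. A patient who was in range throughout treatment, stopped, and then had one routine IGF-I below the limit would be counted with patients who were low while treated.

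The classification is the only operational rule in the effectiveness section, and the percentages are the result of a descriptive study. If GH-deficient patients tend to have low IGF-I once off GH, which is assumed here rather than stated in the documents, the mixing runs mainly towards more low labels. It can build up with follow-up. It would also affect the subgroup columns unequally if stopping differs between subgroups, on which the documents are silent.

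**Working it through.** **Step 1: do the documents allow off-Genotropin values?** Set side by side:

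- Protocol 9.3: the prescription condition applies at inclusion only.
- Protocol 9.5 and 9.10: follow-up ends with withdrawal from the study.
- Protocol 10.2: withdrawal is at the patient's request, or for safety, behavioural or administrative reasons. Stopping Genotropin is not named as ending participation.
- Protocol 11.2: the observation period is one "which must include at least 28 calendar days following the last administration of a drug under study", so some time off drug is foreseen, at least for safety.
- SAP 4.3.1: the action taken with Genotropin is recorded separately from "AE caused patient to discontinue study and outcome".
- SAP 4.4: study duration runs from baseline to the exit date, not to the last dose.

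So patients may stop and stay. Nothing shows how many do.

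**Step 2: does any readable rule remove those values?** SAP 3.1, 4.1, 4.2 and 5 contain none. Taken as written, SAP 4.2 includes them. SAP 4.1 includes them whenever the selected visit falls after stopping.

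**Step 3: how large could it be?** The only figure that can be reproduced is the expected size in protocol 9.10: 600 + 250 + 50 = 900, which agrees. SAP 2.1 reports around 340 patients included when it was finalised. Both serve only to turn percentages into counts.

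Three inputs are assumptions, because the documents give none of them:

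- b = share with at least one low IGF-I while on Genotropin: 10% to 30%
- s = share who stop, stay in the study and have an IGF-I value afterwards: 2% to 20%
- q = chance that such a patient has a low value after stopping: 50% to 90%

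Patients already low on drug keep the same label, so only the remaining 1 − b can change. With off-drug and on-drug results treated as independent:

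added share = s × q × (1 − b); low share as planned = b + s × q × (1 − b)

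| b | s | q | added, points | low share as planned | of 340 | of 900 |
|---|---|---|---|---|---|---|
| 30% | 2% | 50% | 0.02 × 0.5 × 0.7 = 0.7 | 30.7% | 2 | 6 |
| 10% | 5% | 50% | 0.05 × 0.5 × 0.9 = 2.25 | 12.25% | 8 | 20 |
| 10% | 10% | 90% | 0.10 × 0.9 × 0.9 = 8.1 | 18.1% | 28 | 73 |
| 10% | 20% | 90% | 0.20 × 0.9 × 0.9 = 16.2 | 26.2% | 55 | 146 |

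The first and last rows are the ends of the assumed range. If s = 0, the added share is zero.

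**The case against.** The study is descriptive, with no hypothesis test and no comparator. A summary of everything observed in enrolled patients is legitimate, and the low label names a measurement, not a failure of treatment. SAP 6.1 asks for caution in interpretation, and all visits appear in the listings. This stands as a reason to keep the all-observed summary. It does not tell a reader which low labels arose on drug.

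The evidence for long off-drug follow-up is thin. The 28-day text concerns safety reporting, the separate adverse event fields do not prove that patients stop and remain, protocol 9.1 describes subjects receiving Genotropin, and 9.2 leaves participation to the investigator and patient. This also stands: off-drug values are permitted, not demonstrated.

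A rule could sit in the redacted parts of SAP 2.2 and 4.4 or in the separate TLF plan. That cannot be excluded, but SAP 4.2 is readable and says any assessment, and protocol 9.8 assigns operational definitions to the SAP.

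Restricting summaries to patients on drug has its own bias. If patients stop because of adverse events or poor response, those remaining are a favourable selection. This stands and shapes the fix.

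Three stronger readings might be inferred and are not supported:

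- That the yearly tables use every value after baseline. They use one selected visit per window and omit the first 6 months.
- That switching to another GH product produces low IGF-I. Nothing in the documents suggests this; such values raise only the question of which product they describe.
- That the data for an on-treatment flag are certainly in hand. The variable tables list start and stop dates only for GH treatment before baseline. At follow-up they list GH treatment without naming stop date or product.

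**Conclusion.** The point holds as a defect in the definition. As written, SAP 4.2 admits IGF-I values taken after Genotropin has stopped, one low value is decisive, and SAP 4.1 ignores treatment status when choosing visits, while the objective concerns treated patients. The effect is conditional: it needs patients who stop, remain in the study and have a routine IGF-I value afterwards. Its size cannot be derived from the documents. The illustrative 0.7 to 16 percentage points rests wholly on the assumed ranges and on independence of on-drug and off-drug results. If patients who are low off drug were more often low on drug already, the effect would be smaller. The change should be made before database lock; confidence is medium because the number of patients affected is unknown.

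**What to change.** - **SAP 4.2.** Apply rules 1 and 2 to IGF-I values dated while the patient is on Genotropin, using the GH treatment data recorded at follow-up visits. Report the all-observed classification beside it. Align rule 3 with the same period; otherwise a patient whose only values after baseline are off drug would fall through to the within-range group.
- **SAP 4.1.** Keep the all-observed yearly summary. Add an on-Genotropin row and the number of patients off drug in each year. Keep all visits in the listings.
- **First check.** Confirm that the eCRF gives the stop date and the product at follow-up. If it does not, state which stops and switches can be identified and how the rest are handled.

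The cost is some SAP wording and one derived flag. The on-Genotropin rows will hold fewer values and will describe patients who remained on treatment, which the table notes should say.

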### 3.3 SUBGROUPS

- Adult patient of 18 years of age and above and diagnosed with Childhood onset GHD, labeled Childhood onset GHD (CO-GHD)
- Adult patient of 18 years of age and above, not in the CO-GHD group above and diagnosed with GHD before 2013 and previously treated with Genotropin and followed in KIMS®, labeled KIMS GHD (*K-AO-GHD*)
- Adult patient of 18 years of age and above, not in the CO-GHD group above and newly diagnose with GHD, labeled *Naïve-AO-GHD* (N-AO-GHD)

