#### 4.1 BASELINE AND VISIT WINDOW DEFINITION

Baseline is defined as the baseline visit according to the eCRF.

In order to summarize data by year the following visit window definition will be used for follow-up visits:

1. Each visit will be assigned to a yearly measurement according to the principle Year 1 if visit occurred 1 year from baseline visit  $\pm 6$  months. Year 2 if visit occurred 2 year from baseline visit  $\pm 6$  months, and so on. If a patient has more than one visit in a year (as defined here) principle 2 and 3 below will be applied. Visits occurring between baseline visit and baseline visit + 6 months will not be included in summaries by year.
2. Select the visit that has a IGF-1 value.
3. If more than one visit within a year has an IGF-1 value, select the visit with a IGF-1 value closest to the target date. The target date is defined as follows (using Year 1 as an example); Target date for Year 1 is baseline visit plus exactly 12 months (the date occurring 1 year after baseline visit).

The definition of visit windows will be applied in summary tables. Data from all visits will be reported in listings.

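### The IGF-I classification in SAP 4.2 sets no minimum time on Genotropin, so its new-starter and KIMS columns are not like for like

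*SAP*

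**What the plan says.** SAP 4.2 names no endpoint but defines one patient-level classification: "Each patient will be classified according to his/her IGF-I assessments as follows (in hierarchy"). Rule 1 assigns the low label: "If any of the assessments of IGF-I after Swegho baseline visit, are less than the lower limit of normal (LLN"). Rule 2 assigns the high label on the same any-value basis, also counted from the Swegho baseline visit. Rule 3 assigns unknown and changes the time origin: "Else if the patient has no IGF-I reported after Genotropin start". Everyone left over is called within range. On display, the section says: "Where appropriate, the summaries will be presented by subgroups as defined above".

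SAP 3.3 defines the subgroups. N-AO-GHD, which the SAP also calls naïve, is the adult-onset group "not in the CO-GHD group above and newly diagnose with GHD". K-AO-GHD patients were diagnosed before 2013, had already been treated with Genotropin and were followed in KIMS. Protocol section 7 puts median follow-up in KIMS Sweden at about 9 years.

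SAP 4.1 defines yearly visit windows and adds: "Visits occurring between baseline visit and baseline visit + 6 months will not be included in summaries by year". It also says: "The definition of visit windows will be applied in summary tables". SAP 4.2 does not refer to these windows.

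**The concern.** Because rule 1 is tested first and needs only one value, a single low result fixes the label, whatever later results show. It also takes precedence over the high label. A patient who begins Genotropin at or after the baseline visit can receive the low label from a result that reflects the untreated or barely treated state. A KIMS patient cannot, because every counted value comes after earlier treatment.

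This is the only effectiveness classification in the readable SAP, and SAP 2.2 gives long-term treatment outcome as the purpose. No covariates are used (SAP 4.5), so time on treatment is not otherwise taken into account. A difference between the N-AO-GHD and K-AO-GHD columns could be read as a difference in long-term IGF-I control when part of it comes from which phase of treatment was counted.

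**Working it through.** The plan gives no figure for this classification, so there is nothing to reproduce. The check has two parts.

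**1. Tracing the rules**

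- Time on drug: Protocol 9.3 requires only that Genotropin is prescribed at inclusion. SAP 4.3 allows for a first dose that comes after consent. So post-baseline values can include early and even pre-dose values in new starters.
- Visit windows: those in SAP 4.1 are introduced for summaries by year and select one visit per year. Rules 1 and 2 refer to any assessment, so as written the windows do not restrict them.
- Rule 3: take a KIMS patient with IGF-I values transferred from KIMS but none after the Swegho baseline. Rules 1 and 2 find nothing to test. Rule 3 fails, because a value exists after Genotropin start. The patient falls through to within range with no counted value.

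**2. Illustrating the size**

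All inputs are assumptions; none is in the documents.

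- q: chance that a new starter has a low value in the first 6 months (0.1 to 0.5)
- p: chance of a low value per assessment on established treatment (0.02 to 0.10), the same in both groups
- k: later assessments in new starters (4). KIMS patients have k + 1 = 5, all on established treatment.
- Assessments are independent.

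New starters: P(low label) = 1 − (1 − q)(1 − p)^k. KIMS: P(low label) = 1 − (1 − p)^5.

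For p = 0.05, KIMS is 1 − 0.95^5 = 22.6%. New starters with q = 0.2 are 1 − 0.8 × 0.95^4 = 34.8%.

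| p | KIMS | New, q = 0.1 | q = 0.2 | q = 0.3 | q = 0.5 |
|---|---|---|---|---|---|
| 0.02 | 9.6% | 17.0% | 26.2% | 35.4% | 53.9% |
| 0.05 | 22.6% | 26.7% | 34.8% | 43.0% | 59.3% |
| 0.10 | 41.0% | 41.0% | 47.5% | 54.1% | 67.2% |

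The gap runs from 0 points (p = 0.10, q = 0.1) to 53.9 − 9.6 = 44.3 points (p = 0.02, q = 0.5). If the first 6 months after baseline are dropped for everyone, then at p = 0.05 both groups have four values and both give 1 − 0.95^4 = 18.5%.

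**Unequal numbers of assessments.** An any-value rule also rises with the number of values. Keep five for KIMS and give new starters only two later ones, with p = 0.05. The break-even q is 1 − 0.95^5 / 0.95^2 = 1 − 0.95^3 = 14.3%. Below that the gap reverses: q = 0.1 gives 1 − 0.9 × 0.95^2 = 18.8%, against 22.6% for KIMS.

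**The case against.** The strongest reply is that the mechanism needs facts the documents do not supply. Rules 1 and 2 start at the Swegho baseline, not at Genotropin start. Newly diagnosed carries no time limit in the inclusion criteria, and baseline records earlier GH treatment, so some of these patients may have enrolled well after starting. Neither document describes a dose-adjustment phase or says how often early IGF-I is low. All of this stands. It limits the claim to patients who start at or near baseline and leaves the size open.

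A reader might infer that SAP 4.1 and 4.2 contradict each other over the first 6 months. They do not. The exclusion in 4.1 belongs to summaries by year, runs from the baseline visit and applies to every patient; a yearly summary and an ever/never label are different outputs. The sentence applying the windows in summary tables does leave room for doubt, and 4.2 should settle it.

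The study is also descriptive. SAP 6.1 rules out hypothesis tests and urges caution, subgroup display is only where appropriate, and all visits are listed. The protocol's stated comparison is between patients included after 2012 and those included about 15 years earlier, not between these concurrent columns. Part of the SAP is blacked out and the table shells are in a separate document, so the full use of the label cannot be seen. This lowers the stakes: no error rate is affected. It does not repair a descriptive percentage that means different things in adjacent columns, and the caution in SAP 6.1 concerns the lack of a comparator arm.

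**Conclusion.** The point holds as a comparability problem in a descriptive table. With no minimum time on Genotropin, the low and high labels can draw on start-up or pre-dose values in N-AO-GHD patients who begin near baseline, and cannot do so in K-AO-GHD. Separately, the different time origin in rule 3 lets patients with no counted value be shown as within range.

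The size cannot be stated from the documents. The range of 0 to 44 points rests on assumed q and p, independence, equal stable-phase risk and equal numbers of assessments. With fewer assessments in new starters the sign can change.

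A reader might go further and infer that the subgroup contrast would mainly show who was starting treatment, or that new starters would look under-treated. The documents do not support either. They give no early rate and no interval from baseline to first dose, leave visit frequency to investigator and patient (Protocol 9.2), and nowhere equate the low label with under-treatment.

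**What to change.** In SAP 4.2:

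- Rules 1 and 2: count only IGF-I values that are both after the Swegho baseline visit and at least a pre-specified time after Genotropin start. Six months is one option; it matches the length of the SAP 4.1 cut but has a different anchor. State whether the 4.1 windows apply to this table.
- Rule 3: use the same window, so that a patient with no eligible value is unknown and does not fall through to within range.
- Show the early values of new starters in a separate row.
- Report the number of eligible assessments per patient by subgroup. The restriction does not equalise these. In the p = 0.05 illustration, KIMS patients keep five values (22.6%) and new starters four (18.5%), a gap of 4.1 points from the count alone.

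The cost is a sentence or two in the SAP, one derived flag and one extra row. GH treatment and its start date are among the listed variables; for patients whose first dose follows baseline, the programmer should confirm which field holds the Genotropin start. The downside is that some patients with short follow-up move to unknown.

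### SAP 4.2 tests for low IGF-I before high and has no category for both, so the IGF-I ULN count means ever high and never low

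*SAP*

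**What the plan says.** SAP 4.2 first says that there is no pre-specified endpoint, then defines a patient-level classification: "Each patient will be classified according to his/her IGF-I assessments as follows (in hierarchy". Four rules follow, and the first one met decides the label.

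1. "If any of the assessments of IGF-I after Swegho baseline visit, are less than the lower limit of normal (LLN": the label is IGF-I LLN.
2. "Else if any of the assessments of IGF-I after Swegho baseline visit, are greater than the upper level of normal (ULN": the label is IGF-I ULN.
3. "Else if the patient has no IGF-I reported after Genotropin start": the label is IGF-I unknown.
4. "Else the patient will be defined as": within the reference range.

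Rules 1 and 2 use every value after the SWEGHO baseline visit, and one value is enough. No rule covers a patient with both a low and a high value, and no reason is given for testing low first.

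Repeated values are expected. SAP section 4 lists IGF-I as a baseline and follow-up variable. SAP 4.1 provides for several values in one year: "If more than one visit within a year has an IGF-1 value, select the visit with a IGF-1 value closest to the target date". Protocol 9.10 plans long follow-up: "The study is planned to continue for 5 years and each patient entering the study will be included for the whole time period". SAP section 4 gives summary tables one column per subgroup, and SAP 4.2 asks for its summaries by subgroup where appropriate.

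**The concern.** Over several years of follow-up, ever low and ever high are not mutually exclusive. Once rule 1 is met, rule 2 is never applied, so a patient's high values cannot affect the label however many there are. The natural reading of an IGF-I ULN row is the number of patients who went above the upper limit. What the rule counts is the number who went above it and were never below the lower limit.

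The error has one direction: the LLN count is complete and the ULN count can only be too small. This is the only patient-level response classification in the readable SAP, and the study is purely descriptive, so the counts are the result. A count that does not match its label is then a fault in the result itself.

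**Working it through.** **Logic.** The plan gives no figure to reproduce, so the four rules were applied literally to every sequence of low, normal and high post-baseline values of length 1 to 5. The number of sequences of length k with at least one low and one high value is 3^k − 2·2^k + 1, that is 0, 2, 12, 50 and 180 for k = 1 to 5, in total 244. All 244 are labelled IGF-I LLN and none IGF-I ULN. Hence

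n(IGF-I ULN) = n(ever high) − n(both).

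The shortfall is zero only if no patient has both.

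**Size.** The documents give no low rate, high rate, number of values per patient or within-patient correlation. All the inputs here are assumptions: per-visit probability of a high value pH = 10%, of a low value pL = 5% to 15%, and k = 5 values for every patient.

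*Independent visits.*
- P(ever high) = 1 − (1 − pH)^k = 1 − 0.90^5 = 0.4095.
- P(labelled ULN) = (1 − pL)^k − (1 − pL − pH)^k.
- pL = 5%: 0.95^5 − 0.85^5 = 0.7738 − 0.4437 = 0.3301. Share of ever-high patients labelled LLN = 1 − 0.3301/0.4095 = 19%.
- pL = 15%: 0.85^5 − 0.75^5 = 0.4437 − 0.2373 = 0.2064. Share = 1 − 0.2064/0.4095 = 50%.

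*Correlated visits.* Each value is z = √ρ·u + √(1−ρ)·e, where u is a standard normal patient effect and e is standard normal noise. It is low if z < Φ⁻¹(pL) and high if z > Φ⁻¹(1 − pH). Given u, visits are independent, so the formulas above apply with pL(u) and pH(u) and are then averaged over u.

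| Correlation ρ | P(ever high) | P(labelled ULN), pL = 5% to 15% | Share of ever-high labelled LLN |
|---|---|---|---|
| 0 | 0.4095 | 0.3301 to 0.2064 | 19% to 50% |
| 0.3 | 0.3405 | 0.3205 to 0.2655 | 6% to 22% |
| 0.5 | 0.2922 | 0.2883 to 0.2680 | 1% to 8% |
| 0.7 | 0.2396 | 0.2395 to 0.2373 | under 0.1% to 1% |

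With eight values the ranges are 31–70%, 11–35%, 3–15% and about 2% or less. With three values they are 0.6–4% at ρ = 0.5 and under 0.5% at ρ = 0.7.

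*Second model as a check.* IGF-I in SD units with limits at ±2 and five values: between/within-patient SDs of 1.0/0.5, 1.0/1.0 and 0.7/1.2 give shares of 0%, 2% and 11%.

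*In patients.* For about 340 patients (the number in SAP 2.1) with five values each and ρ = 0.5, the number moved is 340 × (0.2922 − 0.2883) = 1 to 340 × (0.2922 − 0.2680) = 8, out of 340 × 0.2922 = 99 ever high.

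**The case against.** **High values are not lost.** SAP section 4 summarises endpoints at baseline and follow-up, including the range, and lists all data; SAP 4.1 lists every visit. This stands, and it limits the point to the patient-level label. It does not remove it: a listing is not a count, and the yearly tables use one selected visit per window.

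**The tables cannot be seen.** SAP 4.2 defines a classification, not a table. The shells are in a separate TLF plan that was not available, which might contain an ever-above-ULN count. The readable SAP does not commit to one. If exclusive categories are needed for grouping, adding one for both meets that need too.

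**The order is declared and the stakes are low.** The SAP says openly that the rules are hierarchical, tests no hypothesis and asks for cautious interpretation. That keeps the point modest, but a reader of the results table will see the label, not the rule.

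**Stronger readings that the documents do not support.**
- A reader might infer that about half of the ever-high patients disappear. That needs independent visits within a patient and 15% low values, neither of which the documents suggest.
- A reader might infer that newly diagnosed patients will falsely look less often high, because early low values fix their label. Subgroups with more early low values could be affected more, but this is speculative: no rates are given, and time on Genotropin at the baseline visit is not stated.
- A reader might infer that a safety signal is being concealed. The SAP places the classification under effectiveness and does not describe values above the limit as over-replacement.
- A reader might see a contradiction with SAP 4.1, where "Visits occurring between baseline visit and baseline visit + 6 months will not be included in summaries by year". That exclusion concerns yearly summaries, and the classification in 4.2 is not yearly.

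**Conclusion.** The point holds as a matter of logic. Followed as written, SAP 4.2 labels every patient with both low and high post-baseline values IGF-I LLN. The IGF-I ULN count therefore understates the number of patients ever above the upper limit, while the LLN count is complete.

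The size is unknown and may be negligible. On the assumed rates with five values it is about 1% or less of ever-high patients at correlation 0.7, 1–8% at 0.5 and 6–22% at 0.3; the 19–50% under independence is an outer limit, not an expectation. It grows with the number of values per patient. Visit intervals are at the discretion of investigator and patient (Protocol 9.2), so that number will vary. The definition should be corrected before the data are presented, but it does not call the underlying IGF-I data into question.

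**What to change.** In SAP 4.2, replace the hierarchy with two separate patient counts: any post-baseline IGF-I below LLN, and any post-baseline IGF-I above ULN. The denominator for both should be patients with at least one post-baseline value. If exclusive categories are wanted, use five: below LLN only; above ULN only; both; always within range; no post-baseline value. Swapping the order of rules 1 and 2 is not a remedy, because it would move the same shortfall to the LLN count.

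The last category also needs one time anchor. Rules 1 and 2 count from the SWEGHO baseline visit, rule 3 from Genotropin start. As written, a patient whose only on-treatment values precede the SWEGHO baseline falls through to within range.

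The cost is one paragraph of SAP text, one table row and a matching change to the TLF plan if it follows the current rule. No new data are needed. The reported figure for patients above ULN may be slightly less favourable. SAP 6.1 places presentation of data after SAP approval and database lock, so the wording should be settled before then.
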